At week 4: AR101 using a standardized IDED regimen of doses of 0.5 mg to a maximum of 6 mg peanut protein (12 mg cumulative) over 5 hours in-clinic (home dosing will be 3 mg/day peanut protein for the next 2 weeks until up-dosing) (Table 1) followed by bi-weekly in-clinic up-dosing from the highest tolerated initial day dose to a maximum of 300 mg/day at home for 22 to 34 additional weeks. If the scheduled bi-weekly up-dosing is not possible, the up-dosing period may be extended by up to 12 weeks to accommodate dose reductions and re-escalation as well as COVID-19 restrictions of in-clinic visits. Thus, the up-dosing period will end at week 28 to 40 (including 4 weeks pretreatment, 22 to 34 weeks of flexible up-dosing, and at least 2 weeks at the maximum dose).

Study Week	Dupilumab/Placebo + AR101
Week 4 (1 to 5 h) IDED	Dose protein (mg)
Q30 min	0.5
	1
	1.5
	3
	6
Cumulative	12

Table 1:	AR101 Initial Dose Escalation Day at Week 4
----------	---

Abbreviations: IDED, initial dose escalation day; Q30, every 30 min

See Section 6.1.1 for details on peanut protein dose escalation.

After 28 to 40 weeks of dupilumab treatment and 24 to 36 weeks of AR101, subjects who achieve 300 mg/day of AR101 for at least 2 weeks will undergo a DBPCFC to assess the level of peanut sensitivity.

Re-Randomization at Week 28 to 40 for Dupilumab Group

Subjects in the dupilumab treatment group from the up-dosing phase will be re-randomized 1:1 placebo or dupilumab regardless of whether they achieve 300 mg/day AR101 for at least 2 weeks at visit 16 or discontinue. However, only those subjects who achieve 300 mg/day AR101 at visit 16 will be eligible to enter the maintenance phase. Subjects who do not achieve 300 mg/day AR101 for at least 2 weeks will enter a 12-week follow-up period. All subjects will have an interactive web response system (IWRS) transaction to maintain the blind.

Double-Blind Maintenance Phase (Only for Subjects Who Reach 300 mg/Day AR101)

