8.5. Method of Treatment Assignment

28 to 40 Week Treatment Phase

Approximately 156 subjects will be randomized at baseline in a 2:1 ratio into one of 2 treatment arms (n=104 to dupilumab and 52 to placebo, in combination with up-dosing of AR101) described in Section 6.1 according to a central randomization scheme provided by an IWRS to the designated

study pharmacist (or qualified designee). Randomization will be stratified by screening peanut-specific IgE level ($\leq 100 \text{ kUA/L}$ or >100 kUA/L) and body weight ($< 30, \geq 30 \text{ kg}$ and < 60 kg, or $\geq 60 \text{ kg}$) at randomization. A minimum of 15 subjects for each weight group will be enrolled.

Maintenance Treatment Phase

At visit 16 (or at the early termination visit for those who discontinue from study prior to visit 16), subjects previously in the dupilumab plus AR101 arm will be re-randomized in a 1:1 ratio into one of 2 treatment arms (dupilumab versus placebo, in combination with AR101), according to a central randomization scheme provided by IWRS. Randomization will be stratified by whether subjects achieve 300 mg/day AR101 for at least 2 weeks by visit 16 (Yes or No). For subjects not achieving 300 mg/day AR101 for at least 2 weeks at visit 16 or early discontinued from study before visit 16, the re-randomization is used to determine their hypothetical assigned treatment for the maintenance phase in order to include them in the intent-to-treatment analysis of visit 22 endpoints. The 24-week maintenance period will start from day 1 of the post up-dosing DBPCFC at visit 16.

Subjects previously in the placebo plus AR101 arm will continue their treatment of placebo plus AR101 in the maintenance phase if they achieve 300 mg/day AR101 for at least 2 weeks at visit 16. To maintain the blinding of treatment assignment, an IWRS randomization call needs to take place for these subjects.

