2. INVESTIGATION PLAN

2.1. Study Design and Randomization

This is a Phase 2, multicenter, randomized, double-blind, parallel-group, 2-arm study in subjects aged 6 to 17 years inclusive who are allergic to peanut. The study consists of a screening period of up to 16 weeks, a 28 to 40-week double-blind treatment period, a 24-week maintenance phase, and a 12-week post-treatment follow-up period. In protocol amendment 3 to accommodate COVID-19 restrictions, double-blind treatment period was extended from 28 weeks to up to 40 weeks. Subjects who attend optional visits between week 28 and week 40 will have increased duration of exposure to AR101 and dupilumab.

Approximately 156 subjects will be randomized at baseline in a 2:1 ratio into one of 2 treatment arms (n=104 to dupilumab and 52 to placebo, in combination with up-dosing of AR101) according to a central randomization scheme provided by an IWRS. Randomization will be stratified by screening peanut-specific IgE level ($\leq 100 \text{ kUA/L}$ or $\geq 100 \text{ kUA/L}$) and body weight ($\leq 30 \text{ kg}, \geq 30 \text{ kg}$ and $\leq 60 \text{ kg}$, or $\geq 60 \text{ kg}$) at randomization. A minimum of 15 subjects for each weight group will be enrolled.

At visit 16 (or at the early termination visit for those who discontinue from study prior to visit 16), subjects previously in the dupilumab plus AR101 arm will be re-randomized in a 1:1 ratio into one of 2 treatment arms (dupilumab versus placebo, in combination with AR101), according to a central randomization scheme provided by IWRS. Randomization will be stratified by whether subjects achieve 300 mg/day AR101 for at least 2 weeks by visit 16 (Yes or No).

Subjects previously in the placebo plus AR101 arm will continue their treatment of placebo plus AR101 in the maintenance phase if they achieve 300 mg/day AR101 for at least 2 weeks at visit 16.

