3.1. The Full Analysis Set (FAS)

FAS includes all randomized subjects. Efficacy analyses will be based on the treatment allocated by the IWRS at randomization (as randomized).

The modified full analysis set (mFAS) includes all FAS subjects who undergo bi-weekly in-clinic up-dosing as described/specified in the protocol and undergo the post up-dosing DBPCFC at Visit 16/Week 28 (a window of -7/+30 days).

The mFAS will be considered as primary analysis set for all efficacy endpoints. The FAS will also be done for all efficacy endpoints as supportive analyses.

FAS-maintenance is a subset of FAS and includes subjects in the FAS who achieve 300 mg/day AR101 for at least 2 weeks in the up-dosing phase and re-randomized based on the treatment allocated by the IWRS at visit 16. The FAS-maintenance is the primary analysis set for efficacy analyses at visit 22.

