5.6. Analyses of Efficacy Variables

The primary efficacy analyses for all the efficacy endpoints will be conducted at Week 28 (visit 16 with a window of -7/+30 days) using the mFAS population. As supportive evidence, the same analysis approach will be repeated with the FAS population at visit 16. The efficacy analyses at visit 22 will be based on the FAS-maintenance population. The analyses of efficacy variables are described in the subsections below and summarized in Section 10.1.

CONFIDENTIAL

Page 39 of 86

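### Visit 22: the protocol re-randomises non-achievers for an intent-to-treat analysis, but the SAP lists only an achievers' set, does not declare the change, and contradicts itself on whether an all-randomised analysis remains

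*SAP*

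**What the plan says.** **Protocol.** Section 6.1 re-randomises the dupilumab group at visit 16 "regardless of whether they achieve 300 mg/day AR101 for at least 2 weeks at visit 16 or discontinue". Section 8.5 stratifies this step by whether 300 mg/day was reached, and gives the reason for including the others: it fixes their "hypothetical assigned treatment for the maintenance phase in order to include them in the intent-to-treatment analysis of visit 22 endpoints". Sections 11.3.1 and 11.4.3 name the mFAS as primary and the FAS as supportive for efficacy. The protocol defines no maintenance subset.

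**SAP.** Section 2.1 keeps the step ("subjects previously in the dupilumab plus AR101 arm will be re-randomized in a 1:1 ratio into one of 2 treatment arms") and the stratum but not the purpose. Section 3.1 creates FAS-maintenance, limited to subjects who reached 300 mg/day for at least 2 weeks, and gives it first rank: "The FAS-maintenance is the primary analysis set for efficacy analyses at visit 22". The same section says: "The FAS will also be done for all efficacy endpoints as supportive analyses". Section 5.6 is narrower: "As supportive evidence, the same analysis approach will be repeated with the FAS population at visit 16", followed by "The efficacy analyses at visit 22 will be based on the FAS-maintenance population". In the table in section 10.1, visit 16 endpoints carry mFAS and FAS, and visit 22 endpoints carry FAS-maintenance alone. Section 2.4 counts subjects who did not reach 300 mg/day as food-challenge non-responders and names no visit. Section 1.2.3, which lists departures from the protocol, has no entry on the visit 22 analysis set.

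**The concern.** Two secondary objectives ask whether dupilumab, continued or stopped, maintains desensitisation compared with placebo at visit 22. The four challenge endpoints that serve them (pass rate and log tolerated dose, for each of the two dupilumab groups) are all comparisons with placebo.

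Reaching 300 mg/day happens after randomisation, may be changed by dupilumab, and is itself a secondary endpoint (SAP 4.5.2). Placebo achievers and dupilumab achievers are therefore selected groups, and the first randomisation no longer makes them comparable. The second randomisation protects only continued versus stopped dupilumab, which is not among the four endpoints.

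At stake is whether the randomisation-protected comparison with placebo, for which the protocol built a re-randomisation stratum, will be produced at all.

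**Working it through.** **1. The texts, question by question**

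- *Do non-achievers enter the visit 22 analysis?* Protocol 8.5: yes, by hypothetical arm. SAP 5.6 and 10.1: no.
- *Is this declared?* SAP 1.2.3 lists changes to objectives, endpoints and period summaries, but not this one.
- *Does a supportive FAS analysis remain?* SAP 3.1: yes, with no visit limit. SAP 2.4 points the same way, because a non-responder rule for non-achievers has no effect in a set that excludes them. SAP 5.6 and 10.1: only at visit 16.
- *In which groups would it be run?* SAP 3.1 analyses the FAS by the treatment the IWRS allocated at randomisation, which has two arms. SAP section 5 lists three maintenance groups. No SAP sentence assigns a dupilumab non-achiever to one of the three through the hypothetical visit 16 assignment.

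**2. The plan's own figure**

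No sample size or power is stated for visit 22. The only stated figure is for visit 16: 65% versus 40%, 2:1, two-sided 5%, 80% power, 156 subjects. The continuity-corrected two-proportion formula gives 52 controls and 3 × 52 = 156. The exact power of Fisher's test at 104/52 is 81.1%. The figure reproduces but does not bear on visit 22.

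**3. How far the two analyses can differ (illustration)**

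Let e be the proportion of an arm that reaches 300 mg/day and enters maintenance, and q the visit 22 pass rate among those who do. Non-achievers count as non-responders.

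- Achiever difference = q(dupilumab) − q(placebo)
- All-randomised difference = e(dupilumab) × q(dupilumab) − e(placebo) × q(placebo)
- If q is equal in both arms, the achiever difference is 0 and the all-randomised difference is q × [e(dupilumab) − e(placebo)].

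Inputs: placebo entry of 80% is suggested by the statement in Protocol section 1 that up to 20% cannot complete up-dosing. Placebo entry of 70%, all dupilumab entry rates and q = 50% to 75% are assumptions.

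| Entry, dupilumab / placebo | Achiever difference | All-randomised, q = 50% | All-randomised, q = 75% |
|---|---|---|---|
| 80% / 80% | 0 | 0.50 × 0 = 0 | 0.75 × 0 = 0 |
| 90% / 80% | 0 | 0.50 × 0.10 = 5 points | 0.75 × 0.10 = 7.5 points |
| 95% / 80% | 0 | 0.50 × 0.15 = 7.5 points | 0.75 × 0.15 = 11.25 points |
| 90% / 70% | 0 | 0.50 × 0.20 = 10 points | 0.75 × 0.20 = 15 points |

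If dupilumab entry were the lower of the two, the signs would reverse.

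Group sizes: all randomised, 104 / 2 = 52 per dupilumab group and 52 on placebo. With 80% entry in every group, FAS-maintenance has about 0.80 × 52 ≈ 42 per group.

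**The case against.** The strongest reply is that the SAP has not dropped anything. Calling FAS-maintenance primary leaves room for a supportive set, and SAP 3.1 supplies one. SAP 2.4 keeps a rule for non-achievers. SAP 5.6.2 says visit 22 pass rates are handled as at visit 16. The rank is known, because protocol and SAP both make the FAS supportive, and the protocol's own primary set was the mFAS, not all randomised subjects. The groups follow from Protocol 8.5 read with the three groups in SAP section 5. Finally, maintenance of desensitisation is naturally asked of those who were desensitised, and visit 22 is descriptive.

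Much of this stands. A reader might infer from SAP 5.6 and 10.1 that the intent-to-treat analysis has been abandoned, or that the SAP is silent on it. The documents do not support that: the SAP contradicts itself, and a supportive rank can be read from it. The achievers' question is also legitimate if labelled as conditional.

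What does not stand is that the matter is settled. The sentence in SAP 5.6.2 covers method, imputation and sensitivity analysis; the set is fixed separately in 5.6. A programmer working from 5.6 and 10.1 would produce no FAS table at visit 22. The link from non-achiever to hypothetical arm has to be taken from the protocol, because the SAP omits it. Descriptive status limits the consequence but does not remove it: Cochran-Mantel-Haenszel and ANCOVA comparisons are planned at visit 22, and SAP section 1 allows inference for the maintenance period if needed.

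**Conclusion.** The point holds as an undeclared departure from Protocol 8.5 and an internal contradiction in the SAP, with a real consequence for what visit 22 estimates. As listed, the comparisons with placebo condition on a post-randomisation outcome. It should be corrected before unblinding. It does not touch the primary claim, and SAP 5.6.3 plans no formal hypothesis for maintenance.

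The size is illustrative. With equal pass rates among achievers of 50% to 75% and entry of 90% versus 80%, the two analyses differ by 5 to 7.5 points; with equal entry they agree at 0. The documents give no entry rate by arm. A reader might infer that restricting to achievers favours dupilumab, but nothing in the documents fixes the direction. Nor do the 40 of 47 subjects who entered maintenance in the follow-on study (Protocol 3.2.1) give an entry rate: that group mixes former placebo subjects, who were up-dosed there, with former AR101 subjects from the originating study.

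**What to change.** - **Add the analysis.** In SAP 3.1, 5.6 and 10.1, specify the four visit 22 challenge endpoints versus placebo on all randomised subjects (FAS), with dupilumab subjects grouped by their actual or hypothetical IWRS assignment at visit 16. State its rank, at least supportive.
- **Missing outcomes.** Count non-achievers and drop-outs as non-responders, with the baseline value for log dose, as SAP 2.4, 5.6.1 and 5.6.2 already provide. Keep the existing multiple imputation for subjects who miss the challenge because of COVID-19. Do not let it override SAP 2.4, since such a change would also reach visit 16.
- **Label and declare.** Describe FAS-maintenance as conditional on reaching 300 mg/day. List the change in SAP 1.2.3, and reconcile the wording in 3.1 that applies mFAS and FAS to every efficacy endpoint.
- **Check assignments.** Before unblinding, confirm that every subject has a visit 16 or early-termination IWRS transaction. Protocol 9.1.3 only asks withdrawn subjects to return, so gaps are possible. Protocol 6.1 provides a transaction for all subjects, so the check can be done blind to arm.

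The cost is SAP wording and a few more tables, with no new data collection. All-randomised pass rates will be lower and will carry the up-dosing effect into visit 22, so both analyses should be shown and labelled.

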3.2. The Per Protocol Set (PPS)

PPS includes all subjects in the mFAS except for those who are excluded because of important protocol violations. An important protocol violation is one that may affect the interpretation of study efficacy results. A preliminary list of such important protocol violations is provided in Section 10.6 and a final list of subjects excluded from FAS will be generated prior to primary analysis database lock. Final determinations of the PPS will be made in the blinded manner before data base lock.

The primary endpoint and first secondary endpoint will be evaluated on the PPS in addition to mFAS and FAS.

3.3. The Safety Analysis Set (SAF)

SAF includes all randomized subjects who receive at least one injection of dupilumab/placebo and be analyzed as treated. Treatment assignment will be based on the actual treatment received not the treatment assigned by IWRS randomization. Treatment compliance/administration for investigational product including both dupilumab/placebo and AR101, as well as all clinical safety variables will be summarized based on SAF.

For the safety analyses during the maintenance period, a subset of SAF which is defined as SAF-maintenance includes re-randomized subjects at visit 16 who received at least one injection of dupilumab/placebo during the maintenance period. Treatment compliance/administration for investigational product and all clinical safety variables during maintenance period will be summarized based on SAF-maintenance.

The actual treatment group as treated is defined by the following rule:

- For a subject randomized to dupilumab Q2W (any dose level), if the subject received all placebo injections, the actual treatment will be assigned as placebo.
- Regardless of the treatment group a subject is randomized to, if the subject received at least 1 dupilumab injection, the actual treatment will be assigned as dupilumab Q2W (any dose level).

For safety summaries, the analysis periods are defined as follows:

- Pre-dosing period (4 weeks) is defined as:
 - Day 1 to the day before the date of AR101 IDED in the up-dosing period if subjects completed the IDED at Week 4
 - Day 1 to early termination (ET) visit date before Week 4 if subjects early terminated from the pre-dosing period
- Up-dosing period (24 to 36 weeks) is defined as:
 - For subjects who entered maintenance period: The date of AR101 IDED to the date of second post up-dosing DBPCFC at visit 16.
 - For subjects who did not enter maintenance period:
 - The date of AR101 IDED at Week 4 to the date of visit 16 if subjects entered follow-up period
 - The date of AR101 IDED at Week 4 to the last dose date of dupilumab/placebo + 14 days if subjects completed dosing to visit 16 but did not enter follow-up period
 - The date of AR101 IDED at Week 4 to early termination (ET) visit date before visit 16 if subjects did not complete dosing to visit 16
- Maintenance period (24 weeks) for subjects who entered maintenance period is defined as:
 - The day after the date of second post up-dosing DBPCFC at visit 16 to the date of second post maintenance DBPCFC at visit 22 if subjects completed the visit 22 with known visit date
 - The day after the date of second post up-dosing DBPCFC at visit 16 to study day 365 (52 weeks times 7 days/week + 1 day) if subjects had missing visit 22 date
 - The day after the date of second post up-dosing DBPCFC at visit 16 to ET visit date before visit 22 if subjects early terminated from maintenance period
- Follow-up period (12 weeks) for subjects who entered follow-up period is defined as:
 - For subjects who completed maintenance period: The day after the date of second post maintenance DBPCFC at visit 22 to the subject end of study visit date or the date of second end of study DBPCFC at visit 25, whichever comes later

- For subjects who did not receive 300 mg/day of AR101 for at least two weeks by visit 16 : The day after the visit 16 date to the subject end of study visit date
- For subjects who early terminated from study treatment in the up-dosing period or maintenance period: The day after the last visit date in the treatment period to the subject end of study visit date
- Overall study period is defined as Day 1 to the date of end of study visit.

The SAF and SAF-maintenance will be the basis for the analyses of the pre-dosing/up-dosing period and maintenance period, respectively; however, for the analyses of the follow-up period, only a subset of the corresponding safety analysis sets will be included, which is defined as the subjects who entered the follow-up period from pre-dosing/up-dosing period and had at least one visit after visit 16 (for SAF) or subjects who entered the follow-up period and had at least one visit after visit after visit 22 (for SAF-maintenance).

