6.4. Visit Windows

Data analyzed by-visit-analysis (including efficacy, laboratory data, vital sign and spirometry/PEF) will be summarized by the study scheduled visits described in the study protocol and SAP, "Schedule of Event". The analysis visit windows will be exhaustive so that all available values obtained from unscheduled visits and early termination (ET) visit have the potential to be summarized.

No analysis visit windows will be applied for the study scheduled visits.

CONFIDENTIAL

Page 56 of 86

The following analysis visit windows will be used to map the unscheduled visits and ET visit, based on the study day:

| Visit | Target Day (TD) | Analysis Time Window Based on Study Day ^a |
|---------------------------|--|---|
| Screening 1 | -113 to -17 | -113 to -17 |
| Screening 1a | -57 to -15 | -57 to -15 |
| Baseline | 1 | 1 |
| Visit 3 (Week 2) | 15 | [2, 22] |
| Visit 4 (Week 4) | 29 | [23, 36] |
| Visit 5 (Week 6) | 43 | [37, 50] |
| Visit 6 (Week 8) | 57 | [51, 64] |
| Visit 7 (Week 10) | 71 | [65, 78] |
| Visit 8 (Week 12) | 85 | [79, 92] |
| Visit 9 (Week 14) | 99 | [93, 106] |
| Visit 10 (Week 16) | 113 | [107, 120] |
| Visit 11 (Week 18) | 127 | [121, 134] |
| Visit 12 (Week 20) | 141 | [135, 148] |
| Visit 13 (Week 22) | 155 | [149, 162] |
| Visit 14 (Week 24) | 169 | [163, 176] |
| Visit 15 (Week 26) | 183 | [177, 190] |
| Following visit 15 | a – 15f are optional visits ^b during | up-dosing period |
| Visit 15a (Week 28) | 197 | [191, 204] |
| Visit 15b (Week 30) | 211 | [205, 218] |
| Visit 15c (Week 32) | 225 | [219, 232] |
| Visit 15d (Week 34) | 239 | [233, 246] |
| Visit 15e (Week 36) | 253 | [247, 260] |
| Visit 15f (Week 38) | 267 | [261, 274] |
| Following windows only ap | ply to subjects who entered doubl | e-blind maintenance period |
| Visit 16 (Week 28 to 40) | Target Day (TD) at last visit during up-dosing period ^c + 14 days | [Visit 16 TD ^d - 8 days, Visit 16 TD + 30 days] |
| Visit 17 (V16 + 4 weeks) | Visit 16 TD + 28 days | [Visit 17 TD – 13 days, Visit 17 TD + 14 days] |

| Visit 18 (V16 + 8 weeks) | Visit 16 TD + 56 days | [Visit 18 TD – 13 days, Visit 18 TD + 14 days] |
|---|---|---|
| Visit 19 (V16 + 12 weeks) | Visit 16 TD + 84 days | [Visit 19 TD – 13 days, Visit 19 TD + 14 days] |
| Visit 20 (V16 + 16 weeks) | Visit 16 TD + 112 days | [Visit 20 TD – 13 days, Visit 20 TD + 14 days] |
| Visit 21 (V16 + 20 weeks) | Visit 16 TD + 140 days | [Visit 21 TD – 13 days, Visit 21 TD + 14 days] |

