| Visit 22 (Week 52 to 64, V16 + 24 weeks) | Visit 16 TD + 168 days | [Visit 22 TD – 13 days, Visit 22 TD + 14 days] |
| Following window | ws apply to subjects who entered | follow-up period |
| Visit 23 (V16 + 28 weeks) | Target Day (TD) at last visit in pre-dosing/up- dosing/maintenance period ^e + 28 days | [Visit 23 TD – 13 days, Visit 23 TD + 14 days] |
| Visit 24 (V16 + 32 weeks) | Target Day (TD) at last visit in pre-dosing/up- dosing/maintenance period + 56 days | [Visit 24 TD – 13 days, Visit 24 TD + 14 days] |
| Visit 25 (Week 64 to 76, V16 + 36 weeks) | Target Day (TD) at last visit in pre-dosing/up- dosing/maintenance period + 84 days | ≥ Visit 24 TD + 14 days |

^a Study day is calculated relative to the date of first study drug injection.

^b Visit 15a – 15f are optional visits in order to reach 300 mg/day AR101 for at least two weeks. Subjects may reach 300 mg/day AR101 for at least two weeks at any of the optional visits.

^c The last visit during up-dosing period could be any of visit 15, 15a, 15b, 15c, 15d, 15e, or 15f.

^dVisit 16 target day (TD) is defined as target day at last visit during up-dosing period + 14 days.

^e The target day at last visit in pre-dosing/up-dosing/maintenance period could be any of the following visit: 1) visit 15 during up-dosing period; 2) ET visit during up-dosing period; 3) visit 22 during maintenance period; 4) ET visit during maintenance period.

In general, the following order will be used to select the record for analysis at given visit:

- 4. Scheduled visit
- 5. ET or end of study (EOS), whichever comes first if scheduled visit not available
- 6. Unscheduled visit if both scheduled visit and ET/EOT/EOS are not available

For the multiple measurements of the same test in the same window, the following rules will be used to select the analysis value:

- If multiple valid values of a variable within an analysis visit window, the closest from the target study day will be selected.
- If the difference is a tie, the value after the targeted study day will be selected.
- If multiple available values of a variable exist within a same day, then the first value of the day will be selected.

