| withdrawal criteria but | illness such as gastroenteritis) | |
| were not withdrawn | | |
| Subject developed | Anaphylaxis resulting in severe hypotension (Appendix 3), | |
| withdrawal criteria but | neurological compromise, or mechanical ventilation secondary to | |
| were not withdrawn | OIT dosing or any food challenge. | |
| Subject developed | Subject develops biopsy-documented EoE or other eosinophilic GI | |
| withdrawal criteria but | disease | |
| were not withdrawn | | |
| Subject developed | Any subject deemed to have a severe allergic reaction or has a life- | |
| withdrawal criteria but | threatening reaction at any time but continues study treatment | |
| were not withdrawn | | |
| Subject developed | Other circumstances such as poor control or persistent secondary | |
| withdrawal criteria but | atopic disease or started beta blockers | |
| were not withdrawn | | |

| Category | Description of Protocol Deviation | Notes |
|-------------------------|--|-------|
| Subject developed | Any infection that is opportunistic, such as active tuberculosis and | |
| withdrawal criteria but | other infections whose nature or course may suggest an immuno- | |
| were not withdrawn | compromised status | |
| Subject developed | Severe laboratory abnormalities that are deemed to be related to | |
| withdrawal criteria but | dupilumab | |
| were not withdrawn | | |
| Subject developed | Diagnosis of a malignancy during the study | |
| withdrawal criteria but | | |
| were not withdrawn | | |
| Subject developed | Evidence of pregnancy | |
| withdrawal criteria but | | |
| were not withdrawn | | |
| Subject developed | Treatment with any prohibited concomitant medication or | |
| withdrawal criteria but | procedure but continued to take study drug | |
| were not withdrawn | Visit 16 was not norformed | |
| Visit not performed | Visit 16 was not performed | |
| Visit not performed | Week 52 Visit 22 (D365) was not performed | |
| Visit not performed | Week 64 Visit 25 EOS (D449) was not performed | |
| Visit not performed | Screening visit 1 (D-113 to D-17) was not performed | |
| Visit not performed | Screening visit 1A (D1 to D-15) was not performed | |
| Visit performed out of | Screening V1 (Day -57 to Day -17) was not performed -57 days of | |
| window | Baseline visit 2 (D1) (up to PA2) | |
| Visit performed out of | Visit 1A was not performed 15 days before visit 2 | |
| window | | |

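### When the visit 22 date is missing, SAP 3.3 ends the maintenance analysis period at a fixed study day 365, which fits only subjects whose up-dosing ended at visit 15 and whose visit 16 was on target (minor)

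*SAP*

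**What the plan says.** SAP 3.3 starts the maintenance analysis period on the day after the second visit 16 challenge and gives three possible ends: the date of the second visit 22 challenge if known, the early termination visit date for subjects who terminated early, and otherwise "to study day 365 (52 weeks times 7 days/week + 1 day) if subjects had missing visit 22 date".

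SAP 6.4 schedules the same visits relative to the subject. The visit 16 target "is defined as target day at last visit during up-dosing period + 14 days", and footnote c lets that last visit be 15 or any of 15a to 15f. Visit 22 is then listed as "Visit 22 (Week 52 to 64, V16 + 24 weeks) | Visit 16 TD + 168 days". Protocol 6.1 (maintenance phase) likewise counts the 24 weeks from day 1 of the subject's own visit 16 challenge.

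For follow-up, SAP 3.3 uses this rule for subjects who completed maintenance: "The day after the date of second post maintenance DBPCFC at visit 22 to the subject end of study visit date". A separate rule, tied to the last on-treatment visit, covers those who stopped treatment: "For subjects who early terminated from study treatment in the up-dosing period or maintenance period: The day after the last visit date". The preliminary deviation list in SAP 10.6 also carries the fixed day: "Week 52 Visit 22 (D365) was not performed".

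**The concern.** Day 365 is the week 52 visit 22 day of a schedule with no extension. The SAP describes extended up-dosing in several places, but this rule was not adapted to it. A subject who reached visit 16 late and has no visit 22 date would have maintenance closed while still inside the planned 24 weeks on treatment.

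The period boundaries feed several outputs. TEAEs are tabulated by period (SAP 5.7.1), event-free times to first AESI are censored at the end of each period (5.7.2), concomitant medications are categorised by period (4.3), and compliance and exposure are computed by period (5.5). For a subject who stayed on treatment, events after day 365 do not move to follow-up either, because the completer rule needs the visit 22 date that is missing. No by-period rule places them.

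**Working it through.** Inputs:
- Stated end: 52 × 7 + 1 = 365 (SAP 3.3), counted from the first study drug injection (SAP 6.4, footnote a).
- Target days of the last up-dosing visit (SAP 6.4): visit 15 = 183; visits 15a to 15f = 197, 211, 225, 239, 253, 267.
- Visit 16 target = last up-dosing target + 14. Visit 22 target = visit 16 target + 168.
- Intermediate visits: "Visit 20 (V16 + 16 weeks) | Visit 16 TD + 112 days" and "Visit 21 (V16 + 20 weeks) | Visit 16 TD + 140 days".
- Visit 16 window: -7/+30 days (protocol Table 4 and its footnote 14).

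The stated figure is reproduced for the unextended case: 183 + 14 + 168 = 365.

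Nominal shortfall = visit 22 target - 365. With the visit 16 window, the shortfall against the actual visit 16 day 1 + 168 runs from nominal - 7 to nominal + 30. A negative value means that day 365 is late.

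| Last up-dosing visit | Visit 16 target | Visit 20 target | Visit 21 target | Visit 22 target | Day 365 early by (target days) | Range with visit 16 window |
|---|---|---|---|---|---|---|
| 15 | 197 | 309 | 337 | 365 | 0 | -7 to 30 |
| 15a | 211 | 323 | 351 | 379 | 14 | 7 to 44 |
| 15b | 225 | 337 | 365 | 393 | 28 | 21 to 58 |
| 15c | 239 | 351 | 379 | 407 | 42 | 35 to 72 |
| 15d | 253 | 365 | 393 | 421 | 56 | 49 to 86 |
| 15e | 267 | 379 | 407 | 435 | 70 | 63 to 100 |
| 15f | 281 | 393 | 421 | 449 | 84 | 77 to 114 |

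On target days, day 365 leaves 365 - 211 = 154 of the 168 days after 15a and 365 - 281 = 84 of 168 after 15f, a loss of 14/168 = 8% to 84/168 = 50%. After 15c to 15f the cut-off precedes the visit 21 target, and after 15e and 15f it also precedes visit 20. Even after 15a it falls before the SAP's visit 22 mapping window opens (379 - 13 = day 366).

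Extension is not the only source of error. After visit 15, visit 16 may fall on day 190 (197 - 7) to day 227 (197 + 30). The 24 weeks then end on day 358 (190 + 168) to day 395 (227 + 168), so day 365 is between 7 days late and 30 days early.

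**The case against.** The strongest counter-argument is about materiality. The rule reaches only subjects who entered maintenance, did not terminate early and have no visit 22 date. Known visit 22 dates and early termination dates have their own correct rules. Events after day 365 still belong to the overall study period (SAP 3.3), remain treatment-emergent (4.6.1) and are listed (5.7.1). No formal hypothesis is attached to maintenance (5.6.3). All of this stands, and it makes the point minor.

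It can also be said that the 6.4 table serves to map unscheduled and early termination visits, and that no analysis windows apply to scheduled visits. That is right as far as it goes: data from scheduled visits 20 and 21 keep their by-visit place. But the table gives the SAP's visit 22 target days, and protocol 6.1 and Table 4 anchor visit 22 on visit 16 in the same way. The inconsistency in the period end remains.

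The 10.6 entry is weak evidence. D365 there labels a visit not performed, in a list stated to be preliminary, and is not an analysis cut-off. The visit 25 entry beside it carries the same kind of unextended day, D449.

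A reader might infer that safety events are lost, that the arms are compared unfairly, or that the 156 - 122 = 34 subjects outside the planned primary analysis set are the ones affected. The documents support none of these. The events are kept elsewhere, and the rule is the same in every arm with nothing to show differential missingness. The 34 do not identify extended subjects, because visit 16 after 15a or 15b (days 211 and 225) is still within the week 28 window to day 227. A missing visit 22 date is also required.

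**Conclusion.** The rule is wrong as written, but minor. Followed exactly, it gives the wrong end of maintenance for most schedules the SAP allows: 14 to 84 days early on target days after visits 15a to 15f, and from 7 days late to 30 days early after visit 15 once the visit 16 window is counted. The target-day figures assume that visits fall on their SAP targets; real gaps will vary with the window.

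The consequence is confined to by-period safety outputs: maintenance TEAE and exposure tables, AESI censoring, and an undefined follow-up start for subjects who stayed on treatment. Subjects who stopped treatment in maintenance do have a follow-up start. Efficacy, including the visit 22 challenge endpoints, does not use this period end. The documents do not give the number of affected subjects, and it may be zero.

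**What to change.** In SAP 3.3, replace the fixed day for a missing visit 22 date by a subject-specific end: day 1 of the actual visit 16 challenge + 168 days, in line with protocol 6.1. Extend it to the last study treatment date if dosing continued beyond that day, so that on-treatment time is not pushed into follow-up. Cap it at the last visit or contact, so that unobserved time is not credited to maintenance.

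Add the matching follow-up rule: for subjects with a missing visit 22 date who stayed on treatment and entered follow-up, follow-up starts the next day. Keep the existing rule for subjects who stopped treatment in maintenance.

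Optionally, and for consistency only, express both D365 (visit 22) and D449 (visit 25) in SAP 10.6 relative to visit 16.

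The cost is about two sentences in SAP 3.3, two optional labels in 10.6 and the matching programming before database lock. Data collection and study conduct do not change.
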